6.6. Interim Analyses and Data Monitoring

6.6.1. Planned Interim and Early Analyses

A DSMB will monitor ongoing results to ensure subject well-being and safety as well as study integrity. The DSMB will be asked to recommend early termination or modification only when there is clear and substantial evidence of a treatment difference.

6.6.2. Interim Safety Review

Safety analyses will evaluate Grade 3 and 4 AE and SAEs by treatment arm. Safety monitoring will be ongoing with the DSMB reviewing safety data approximately every one to two weeks during the study. The unblinded statistical team will prepare these reports for review by the DSMB.

6.6.3. Interim Efficacy Review

The time of the interim efficacy analysis for ACTT-4 will be assessed by enrollment 1.5 months after the first enrollment:

- If the study reaches or exceeds 1/3 of total enrollment within 1.5 months (assumes slightly slower enrollment at the beginning), no interim efficacy analysis will be performed.
- If the study does not reach 1/3 of total enrollment within 1.5 months, an interim analysis will occur after the first third of enrolled subjects have reached Day 29.

If an interim efficacy analysis is performed, the Lan-DeMets spending function analog of the O'Brien-Fleming boundaries will be used to monitor the primary endpoint as a guide for the DSMB with an overall two-sided type-I error rate of 0.05.

Specifically, two one sided boundaries are constructed at level 0.025 using the spending function

$$\alpha^*(t) = 2[1 - \Phi\{2.241/t^{\frac{1}{2}}\}],$$

where Φ is the standard normal distribution function. Lan-DeMets software from the University of Wisconsin, now available in the R package 'ldebounds', will be used to calculate boundaries. The planned boundaries at 33% and 100% of information on the z-scale are ± 3.7307 (nominal $p = 0.00019153$) and 1.9605 (nominal $p = 0.049937$).

All available data at the time of lock will be included in the Interim Efficacy data. Subjects who are on-study but have not yet completed the Day 29 study visit will also be included but will be censored at their last assessment unless they have progressed to mechanical ventilation or died.

Conditional power will be presented as an additional guide to the DSMB. Conditional power allows computation of the probability of obtaining a statistically significant result by the end of the trial given the data accumulated thus far, incorporating and assuming a hypothesized treatment effect (e.g., the treatment effect assumed for sample size determination) thereafter. If conditional power is less than 20% when assuming the trial's design assumptions, consideration should be given to stopping the trial.

The unblinded statistical team will prepare these closed session reports for DSMB review and recommendations. Analyses will be presented with blinded codes for treatment arms to protect against the possibility that the DSMB report may fall into the wrong hands. A DSMB Charter will further describe procedures and membership.

6.7. Multicenter Studies

Data will be pooled across all clinical sites. Secondary analyses of the primary outcome will account for site via stratification by geographic region as noted in Section [6.4](#).

[figure not shown]
A sensitivity analysis of the primary outcome will be performed to assess the impact of individual sites on the observed treatment effect. Letting M be the total number of sites, the primary analysis will be repeated by excluding a single clinical site and performing the analyses on the remaining $M-1$ sites. This process will be repeated so that estimates are generated for each of the $M-1$ subset datasets. Presentations from these analyses are described in Section [8.2.1](#).

6.8. Multiple Comparisons/Multiplicity

A fixed sequence testing scheme will control the overall family-wise Type I error rate at a two-sided α level of 0.05. If the primary hypothesis is rejected at two-sided $\alpha < 0.05$, hypothesis testing will proceed to four key secondary endpoints. Hypothesis testing will follow the fixed ordering below ([Figure 1](#)):

Figure 1: Elements of the fixed-sequence hierarchical testing procedure

- 1) Mechanical Ventilation-Free Survival by Day 29 (i.e., Proportion not progressing to ordinal scale 7 or 8)
- 2) Day 15 Clinical Status Ordinal Score;
- 3) Proportion not progressing to ordinal scale 6, 7 or 8 (amongst actual baseline Clinical Status ordinal scale 5 only);
- 4) Overall mortality (Day 29); and
- 5) Time to recovery (Day 29).

Hypothesis testing will continue at the next endpoint with $\alpha = 0.05$ only if the previous hypothesis is rejected at $\alpha=0.05$. This method of carrying forward the α -level from the previous test is described in the FDA guidance on Multiple Endpoints in Clinical Trials [<https://www.fda.gov/regulatory-information/search-fda-guidance-documents/multiple-endpoints-clinical-trials-guidance-industry>]. See Section 8.1.2 for details on the sequence of hierarchical analyses.

There is no planned multiplicity adjustment for the evaluation of safety (Section 9) or additional sensitivity or additional secondary efficacy (Section 8.2) or exploratory (Section 8.3) analyses.

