As noted in Section 6.6.3, to maintain an overall two-sided type-I error rate of 0.05, the Lan-DeMets spending function analog of the O'Brien-Fleming boundary will be used to derive the cumulative error spending and boundaries for the interim analysis.

For the final analysis, square-root of the test statistic and p-value from a standard normal distribution function will be calculated using the pseudocode and formulae provided in Section 6.1 and compared to the final boundary and nominal p-value as determined using the 'ldlbound' package listed in Section 6.6.3.

If the trial is stopped at the interim analysis, then to derive the p-value and confidence intervals for the early and final analysis sets, stage-wise ordering of the sample space will be used [3]. The resulting p-value, proportions, and confidence interval will be presented in the final report.

A graphical hierarchical design will be used to control the study-wide alpha as described in Section 6.8. This will not change the construction of p-values or their interpretation for the primary analysis, but will influence secondary analyses listed in Section 8.1.2.

Kaplan-Meier curves (Figure 4) and p-values with estimates of mechanical ventilation-free survival at 28 days will be calculated and accompanied by confidence intervals adjusted to be consistent with the nominal alpha level at the interim or final analysis and constructed using the complementary log-log transformation.

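### Section 6.8 claims family-wise control at 0.05, but only the primary has a group-sequential boundary, so control of the secondaries fails slightly if an interim efficacy look is taken

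*SAP*

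**What the plan says.** Section 6.8 claims two-sided 0.05 control over the primary and four ordered secondaries: "A fixed sequence testing scheme will control the overall family-wise Type I error rate". The step rule is one sentence for all cases: "Hypothesis testing will continue at the next endpoint with $\alpha = 0.05$ only if the previous hypothesis is rejected". The hierarchy opens when the primary is rejected at a two-sided level below 0.05.

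Section 6.6.3 makes one interim efficacy look conditional on slow enrolment: in that case "an interim analysis will occur after the first third of enrolled subjects have reached Day 29". The Lan-DeMets O'Brien-Fleming boundaries apply to the primary ("boundaries will be used to monitor the primary endpoint as a guide for the DSMB"), "with an overall two-sided type-I error rate of 0.05". The values given are ±3.7307 at 33% information (nominal p 0.00019153) and 1.9605 at 100% (nominal p 0.049937).

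Section 8.1.1 keeps the early-stop path open ("If the trial is stopped at the interim analysis") and prescribes stage-wise ordering there, under the primary analysis. Section 6.1 adjusts the primary confidence interval for the sequential design but keeps plain 95% intervals for the secondaries, and section 8.1.2 repeats 95%. No boundary or alpha spending for any secondary appears in the SAP.

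**The concern.** A fixed sequence that passes the full level to the next hypothesis is valid when all hypotheses are tested at one fixed analysis. With an efficacy look, the analysis at which a secondary is tested depends on when the primary crosses its boundary. If the two statistics are positively correlated, an early crossing by the primary selects data in which a truly null secondary also tends to be extreme, and that secondary is then compared with an unadjusted 1.96.

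Positive correlation is plausible here. The Day 15 ordinal score, progression to categories 6 to 8, and mortality share the ordinal scale or the deaths with the primary. What is at stake is the unconditional control claim in 6.8, on which any confirmatory statement about a secondary rests.

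**Working it through.** **Step 1: the plan's boundaries.** Inputs from 6.6.3: two one-sided boundaries at 0.025, with spending function α*(t) = 2[1 − Φ(2.241/√t)] and t = 0.33.

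- 2.241/√0.33 = 3.901, so α*(0.33) = 0.0000958 per side, or 0.0001915 two-sided. The interim boundary is z = 3.730.
- Solving for the final boundary by numerical integration gives z = 1.9605 (nominal p 0.04993).

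The stated values reproduce.

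**Step 2: primary drift in the SAP's own scenarios.** Inputs from section 5, Table 1: 1382 subjects, so 691 per arm. Drift d = (p₂ − p₁)/√(2p̄(1 − p̄)/691).

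- 0.85 vs 0.90 (design effect): 0.05/√(2·0.875·0.125/691) = 2.81
- 0.90 vs 0.95: 0.05/√(2·0.925·0.075/691) = 3.53
- 0.85 vs 0.925: 0.075/√(2·0.8875·0.1125/691) = 4.41

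**Step 3: error for a null secondary.** Let X₁, X₂ be the primary z-statistics at the two looks, with means d√t and d. Let Y₁, Y₂ be those of a secondary with no effect. X and Y have correlation ρ at the same look, and each has correlation √t between looks. Following 6.8, the secondary is tested once. It is rejected if

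- |X₁| ≥ 3.7307 and |Y₁| ≥ 1.96, or
- |X₁| < 3.7307, |X₂| ≥ 1.9605 and |Y₂| ≥ 1.96.

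The assumptions are that the look is taken and its boundary followed, that t = 0.33 holds for both endpoints, and that the secondary is the step right after the primary. The SAP gives neither ρ nor the secondary information fraction, so ρ is shown as a range. Simulation with 3 million draws (Monte Carlo standard error about 0.0001) gives this two-sided error:

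| Drift | ρ = 0.5 | ρ = 0.7 | ρ = 0.85 | Chance of interim stop |
|---|---|---|---|---|
| 2.8 (design effect) | 0.0355 | 0.0326 | 0.0323 | 1.7% |
| 3.56 (near 0.90 vs 0.95) | 0.0454 | 0.0436 | 0.0420 | 4.6% |
| 4.5 (near 0.85 vs 0.925) | 0.0530 | 0.0552 | 0.0563 | 12.7% |
| 5.0 (beyond Table 1) | 0.0539 | 0.0565 | 0.0574 | 19.6% |

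The maximum found is 0.0575, at ρ = 0.85 and drift 4.8, where the chance of an interim stop is about 17%. At ρ = 0 the maximum is 0.050, so there is no inflation. At the design effect the error stays below 0.05 because the secondary is reached only when the primary succeeds. With ρ = 0 that is about 0.80 × 0.05 = 0.040.

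**Step 4: does a boundary for the secondaries repair it?** Testing them at 3.7307 and 1.9605 gives a maximum two-sided error of 0.0499. A Pocock-type boundary (2.203 at both looks, nominal p 0.0276) gives at most 0.031 over the points checked (ρ = 0.5, 0.8, 0.9, 1.0; drift 3 to 6). Both control the error.

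**The case against.** The other side has several fair points.

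- **The rule after an early stop is inferred.** The SAP nowhere says outright that secondaries are tested at 0.05 after an interim stop, and 6.2.2 places the final analyses on the full locked database. This stands as a caution on wording. The inference follows from one rule without exception, and nothing in the SAP exempts or adjusts the secondaries.
- **A secondary would probably have more than one third of its information at a stop.** Section 6.6.3 includes all available data, and the look waits for Day 29 of the first third with no enrolment pause mentioned. If the secondary is tested at an assumed fraction of 0.5, the maximum for ρ from 0.5 to 1 falls to 0.052–0.054. At 0.6 it is 0.051–0.053. This stands and reduces the size.
- **The point may be moot.** The look depends on slow enrolment. Section 15.3 says all subjects were enrolled by version 2.0, and section 6.2.1 mentions a futility analysis in April 2021. Neither says whether the efficacy look took place, and a futility stop would not open the hierarchy. This stands as a limit on practical effect, while 6.6.3, 6.8 and 8.1.1 still carry the early-stop path.

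A reader might infer that each secondary gets two tries at 1.96, with the crude two-look error of 0.088. The SAP does not support that: a secondary is tested once, at the look where the primary is rejected. A reader might also quote one-direction errors, which exceed their nominal 0.025 even at the design effect (0.027 to 0.032 for ρ from 0.5 to 0.85). The claim in 6.8 is two-sided 0.05, and it should be judged on that scale.

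**Conclusion.** The point holds in a limited form. As written, 6.8 does not deliver strong two-sided 0.05 control if an interim efficacy look is taken and the trial can stop on it. With equal information fractions of 0.33 and a correlation of 0.5 to 0.85, the error for a null secondary is about 0.053 to 0.056 in the SAP's 0.85 versus 0.925 scenario, and about 0.0575 at worst. There is no two-sided excess at the design effect, less with overrun data, and none without an efficacy look. The primary analysis is not affected. A repair is still worthwhile, because the control claim is unconditional and the correction is short.

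**What to change.** In 6.8, state whether the interim efficacy look took place.

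- **If it did not:** say so and keep 0.05 for the secondaries.
- **If it did or could:** test each secondary, once reached in the hierarchy, against its own group-sequential boundary at its own information fraction. Lan-DeMets O'Brien-Fleming is one choice (about 3.73 at one third and 1.9605 at the end). A Pocock-type boundary is also valid. Specify how overrun data enter the information fraction.
- **Gate for the primary:** replace the general criterion of a two-sided level below 0.05 with the nominal levels in 6.6.3 (0.00019153 at the interim, 0.049937 at the end).

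The cost is a few sentences of SAP text. With the O'Brien-Fleming choice the loss at the final analysis is negligible (1.9605 against 1.96). The real downside is that secondaries are less likely to reach significance after an early stop.

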7. STUDY SUBJECTS

7.1. Disposition of Subjects

A summary of the reasons that subjects were screened but not randomized will be tabulated ([Table 2](#)).

The composition of analysis populations, including reasons for subject exclusion will be summarized by treatment group and actual baseline ordinal score ([Table 3](#)). A subject listing of subjects excluded from the As Treated Population will be generated ([Listing 1](#)).

The disposition of subjects will be tabulated by treatment group and actual baseline ordinal score ([Table 4](#)). Study milestones included in the table will include, but not limited to: the total number of subjects that were randomized, completed expected blood draws, completed Study Visit Day 15, completed Study Visit Day 22, and completed Study Visit Day 29. For the calculation of percentages, subjects who die will not be included in the denominators for visits/assessments beyond their death. Subject status at study termination will be summarized by treatment group and baseline ordinal score ([Table 5](#)).

Treatment exposure will be summarized by treatment group ([Table 6](#), [Table 7](#), and [Table 8](#)). Summaries of prior remdesivir treatment, prior remdesivir, and prior dexamethasone treatment by treatment group and actual baseline ordinal score will also be provided ([Table 9](#), [Table 10](#), and [Table 11](#)).

A flowchart showing the disposition of study subjects, adapted from the Consort Statement [1] will be generated ([Figure 2](#)). This figure will present the number of subjects screened, randomized, lost to follow-up, and analyzed, by treatment group and actual baseline ordinal score (ordinal scale 5, 6.). The number of subjects that terminated early by hospitalization status at the time of the last ordinal score collection will be summarized graphically ([Figure 3](#)).

A listing of subjects who discontinued dosing or terminated study follow-up and the reason will be generated ([Listing 2](#)). A listing of subjects who received incorrect treatment and a listing of subjects who were randomized to the incorrect stratum will also be generated ([Listing 5](#) and [Listing 6](#)).

The disposition of subjects at Day 60 will be tabulated by treatment group and actual baseline ordinal score ([Table 12](#)).

7.2. Protocol Deviations

Subject-specific protocol deviations will be summarized by the reason for the deviation, the deviation category, treatment group, and actual baseline ordinal score ([Table 13](#)). A summary of major deviations will also be generated ([Table 14](#)). All subject-specific protocol deviations and non-subject specific protocol deviations will be included in listings ([Listing 3](#) and [Listing 4](#)).

8. EFFICACY EVALUATION

8.1. Primary Efficacy Analysis

8.1.1. Primary Analysis of Mechanical Ventilation-Free Survival

The primary efficacy analysis will be performed in the mITT population and is a test of superiority of the proportion of participants with invasive mechanical ventilation free survival, between the two treatment groups at Day 29 (Table 15). The test statistic will be a large sample test of the difference in Kaplan-Meier estimates of the 28-day probability of mechanical ventilation free survival with a two-sided type I error rate of 0.05. The test of difference will assume asymptotic normality and use Greenwood's variance formula. The primary analysis will utilize a test statistic adjusting by actual baseline Clinical Status ordinal score strata [2] (Klein 2007) and be based on the weighted complementary log-log transformation of the Kaplan-Meier estimator. The two primary baseline Clinical Status strata will be patients with baseline ordinal score 5 or baseline ordinal score 6.

The primary analysis will utilize a test statistic adjusting by actual baseline ordinal score ordinal score strata (Klein 2007) and be based on the complementary log-log transformation of the Kaplan-Meier estimator.

The test statistic to be used is, as in Klein 2007:

$$X_{\text{STRAT}}^2 = \frac{\left(\sum_{s=1}^3 \hat{w}_s (\log(-\log(\hat{S}_{1s}(t))) - \log(-\log(\hat{S}_{2s}(t)))) \right)^2}{\sum_{s=1}^3 \hat{w}_s^2 (\hat{V}(\log(-\log(\hat{S}_{1s}(t)))) + \hat{V}(\log(-\log(\hat{S}_{2s}(t)))))}$$

Where $\hat{V}(\cdot)$ is the estimated variance of the transformed survival function which is equal to $\hat{\sigma}_{ks}(t)^2 / (\log(\hat{S}_{is}(t)))^2$ for the treatment group k and strata s and where $\hat{\sigma}_{ks}(t)^2$ is estimated using Greenwood's formula:

$$\hat{\sigma}_{ks}(t)^2 = \sum_{t_{kst} \leq t} \frac{d_{ksi}}{Y_{ksi}(Y_{ksi} - d_{ksi})}$$

And $k = 1, 2$ is the treatment group, $s = 1, 2$ is the actual baseline Clinical Status strata, $\hat{S}_{ks}(t)$ is the estimated survival at time $t = 28$ and \hat{w}_s is inverse variance of the difference divided by the sum of inverse variances of the difference.

This test-statistic follows a Chi-square distribution with 1-degree of freedom or, alternatively, the square-root follows a standard-normal distribution.

As noted in Section 6.6.3, to maintain an overall two-sided type-I error rate of 0.05, the Lan-DeMets spending function analog of the O'Brien-Fleming boundary will be used to derive the cumulative error spending and boundaries for the interim analysis.

For the final analysis, square-root of the test statistic and p-value from a standard normal distribution function will be calculated using the pseudocode and formulae provided in Section 6.1 and compared to the final boundary and nominal p-value as determined using the 'ldlbound' package listed in Section 6.6.3.

If the trial is stopped at the interim analysis, then to derive the p-value and confidence intervals for the early and final analysis sets, stage-wise ordering of the sample space will be used [3]. The resulting p-value, proportions, and confidence interval will be presented in the final report.

A graphical hierarchical design will be used to control the study-wide alpha as described in Section 6.8. This will not change the construction of p-values or their interpretation for the primary analysis, but will influence secondary analyses listed in Section 8.1.2.

Kaplan-Meier curves (Figure 4) and p-values with estimates of mechanical ventilation-free survival at 28 days will be calculated and accompanied by confidence intervals adjusted to be consistent with the nominal alpha level at the interim or final analysis and constructed using the complementary log-log transformation.

8.1.2. Hierarchical Sequence of Secondary Endpoints Analyses

Analyses described in this section will be subject to the fixed-sequence hierarchical testing procedure described in Section 6.8. Any reference to p-values in this section is conditional on preceding hypothesis tests in the hierarchy.

If a superior test fails to reject the null hypothesis, the analyses will still be performed to provide estimated effects with confidence intervals for relevant statistics and associated confidence-interval by-arm, but p-values will not be generated. Confidence intervals for all analyses of secondary endpoints, will be 95% confidence intervals.

8.1.2.1. Clinical Status Ordinal Scale at Day 15

In the mITT population, the distribution of the 8-point Clinical Status ordinal score at Study Visit Day 15 (not necessarily actual study day 15), will be analyzed using a proportional odds model with treatment arm and actual baseline ordinal score (baseline ordinal score 5 or baseline ordinal score 6) as covariates. The treatment odds ratio estimated from the model will be presented along with the p-value, (Table 21). This analysis will be repeated for the As Treated population (Table 22). The Study Visit Day 15 clinical status score will be depicted graphically using shifted bar plots; the outcomes will be presented by actual baseline ordinal score and treatment group (Figure 13).

8.1.2.2. Proportion of Subjects Not Progressing to Clinical Status 6, 7, or 8 by Day 29

In the mITT population and among only those with an actual baseline ordinal score of 5, the proportion of subjects not progressing to ordinal score 6, 7, or 8 by Day 29 (see Section 3.3.4) will be analyzed using the same modeling approach as the primary outcome and described in Section 8.1.1. Kaplan-Meier curves (Figure 31) and p-values with estimates of proportions at the Day 29 study visit will be calculated and accompanied by confidence intervals (Table 23).

8.1.2.3. Mortality by Day 29

Mortality through Day 29 will be analyzed as a time to event endpoint (see Section 3.3.5). A table will present median time to event along with 95% confidence intervals overall for each treatment arm along with the hazard ratio estimate and log rank p-values. Differences in time-to-event endpoints by treatment will be summarized with Kaplan-Meier curves (Figure 27).

